3.1 Study Design

The study is an open-label, phase 2 trial treating subjects with first or second relapse of multiple myeloma who were refractory to prior lenalidomide treatment and may have been exposed to prior daratumumab **or other anti-CD38 antibody therapy**. Based on available information for this study population, **the reference rate listed in the protocol section 4.2 indicates the ORR was considered to be 60%, while for MRD[-]CR was considered to be 3%.**

Subjects may receive treatment until progression. Myeloma disease status will be monitored locally for response and progression per International Myeloma Working Group (IMWG) criteria (Kumar et al, 2016) every 28 ± 7 days from cycle 1 day 1 until

confirmed progressive disease (PD), death, lost to follow-up, or withdrawal of full consent (whichever occurs first), regardless of cycle duration, dose delays or treatment discontinuation.

Subjects with a suspected CR or better will have a bone marrow for minimal residual disease (MRD) assessment at 12 and 24 months (\pm 4 weeks) from start of treatment (unless an MRD assessment was performed within 4 months before planned assessment).

Subjects who end study drug(s) without confirmed PD are required to complete disease response assessments and report new antimyeloma treatment every 28 ± 7 days until first subsequent antimyeloma treatment, death, lost to follow-up, withdrawal of full consent, confirmed PD, or end of study, whichever occurs first. Subjects, who discontinue treatment and either start new antimyeloma treatment or have PD, will enter long-term follow-up every 12 weeks until death or end of study.

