4.2 Subgroups

ORR and PFS will be examined for the below subgroup analysis. When there is not a sufficient number of subjects in the subgroup, i.e., less than 10% of the whole population, the subgroup analysis will not be conducted:

- prior carfilzomib exposure (yes, no)
- number of prior lines of therapy (1, 2)
- timing of lenalidomide refractoriness (during maintenance: yes, no)
- **Cytogenetic risk measured by FISH (high risk (t(4;14), t(14;16), deletion 17p), standard risk)**
- **R-ISS (stage I, stage II, stage III)**
- **Prior anti-CD38 exposure (yes, no)**
- **Refractory to prior anti-CD38 treatment (yes, no)**
- **Prior bortezomib exposure (yes, no)**
- **Refractory to prior bortezomib treatment (yes, no)**

5. Definitions

Baseline

The baseline value is defined as the last assessment prior to the first dose of **any study treatment**. Absolute change from baseline will be defined as (post baseline value - baseline value). Relative change from baseline will be defined as (post baseline value - baseline value)/baseline value * 100%.

Complete Response Rate (CRR)

CRR is defined as the proportion of subjects whose best overall response is sCR or CR.

Cytogenetic Risk group as determined by Fluorescent in Situ Hybridization (FISH)

The FISH data will be used to determine the cytogenetic risk group as following:

High risk group: Subjects who have the cytogenetic abnormalities t(4;14) or t(14;16), and/or deletion 17p.

Standard risk group: Subjects who do not have any of the cytogenetic abnormalities t(4;14), t(14;16) and deletion 17p.

Missing: Subjects who cannot be identified as high risk nor standard risk.

Duration of Response (DOR)

DOR is defined as the time from first evidence of PR or better per IMWG-URC to the earliest of disease progression or death due to any cause for subjects with a best response of PR or better. DOR will be censored as per the PFS endpoint. Please see [Table 5-1](#)

$$\text{DOR} = [(\text{PD or death date whichever occurs first}) \text{ or date of censoring if censored} - \text{response start date} + 1] / 30.4.$$

End of Study

The end of study date is defined as the date when the last subject across all sites is assessed or receives an intervention **for evaluation in the study (ie, last subject last visit), including any additional parts in the study (eg, long-term follow-up, additional antibody testing), as applicable.** The study will end 4 years after the last subjects is enrolled in the study.

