
Number of doses of pomalidomide administered

It is defined as the total number of non-zero doses of pomalidomide a subject received during the treatment period of the study

Number of doses of dexamethasone administered

It is defined as the total number of non-zero doses of dexamethasone a subject received during the treatment period of the study

Overall Response (OR)

OR is the best overall confirmed response of partial response (PR), very good partial response (VGPR), complete response (CR), or stringent complete response (sCR).

Overall Response Rate (ORR)

Overall Response Rate (ORR) is defined as the proportion of subjects that reach the overall response among all subjects who received at least 1 dose of the carfilzomib.

Overall Survival (OS)

OS is defined as time from start of treatment until death from any cause.

$OS = (\text{Death date or date of censoring if censored} - \text{start of any study treatment date} + 1) / 30.4$

Subjects still alive will be censored at the date last known to be alive. If the date last known to be alive is after the date that triggers the analysis (ie, the data cutoff date), the subject will be censored at the analysis trigger date.

Progression Free Survival (PFS)

PFS is defined as the time from the first dose date of any study treatment until the first documentation of disease progression or death due to any cause, whichever occurs first in the absence of subsequent anticancer therapy and if not > 70 days from the last non-NE, post-baseline disease assessment. PFS will be censored at the last non-NE, post-baseline disease assessment or the earlier of the following, where applicable: (a) the last non-NE, post-baseline disease assessment prior to subsequent anticancer therapy, or (b) the last non-NE, post-baseline assessment followed > 70 days later by disease progression or death; otherwise, at first dose date. Disease progression is based on the IMWG-URC [2016].

PFS time in months= [(PD or death date, whichever occurs first) or date of censoring if censored– start of treatment date + 1] / 30.4.

Table 5-1. Conventions for Censoring for PFS

Situation	Date of Progression or Censoring	Outcome
No PD or death, no new anticancer treatment	Last visit; otherwise, first dose date of any study treatment	Censored
No PD or death, new anticancer treatment	Last visit prior to new treatment; otherwise, first dose date of any study treatment	Censored

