PD or death > 70 days after last visit	Last visit prior to PD or death; otherwise, first dose date of any study treatment ^a	Censored
PD or death, no prior new anticancer therapy	Earlier of PD or death ^b	Event
No PD, new anticancer treatment, death	Last visit prior to new treatment; otherwise, first dose date of any study treatment ^b	Censored

“Visit” refers to a post-baseline evaluable disease assessment.

^aIf new anticancer therapy starts prior to PD or death, PFS will be censored at the earliest of the following: (a) the last evaluable disease assessment prior to subsequent anticancer therapy, or (b) the last non-NE, post-baseline assessment followed > 70 days later by disease progression or death; otherwise, first dose date.”

^bPFS will be censored if PD or death > 70 days after last evaluable disease assessment.

Relative Dose Intensity

RDI reflects whether the dose intensity of a therapy was implemented as planned. It will be calculated as the ratio of actual dose intensity relative to planned dose intensity

$$\text{Relative Dose Intensity (RDI)} = \frac{\text{Actual dose intensity}}{\text{Planned dose intensity}}$$

For carfilzomib: Actual dose intensity is defined as the actual amount of drug in mg/m² delivered to a subject per week of treatment.

$$\text{Actual Dose Intensity (mg/m}^2\text{/week)} = \frac{\text{Actual cumulative dose (mg/ m}^2\text{)}}{\text{Number of weeks of actual treatment}}$$

Actual cumulative dose in (mg/m²) is the sum of received doses (mg) divided by baseline body surface area (BSA) (m²) of the patient. Each subject's first dose of carfilzomib will be calculated based upon baseline BSA using the Mosteller formula. The dose for each subject should not be revised unless the subject experiences a change in body weight of > 20% in which case the BSA and dose should be recalculated. The recalculated BSA becomes the new baseline and is used in dose calculation. BSA will be capped at 2.2 for carfilzomib. Number of weeks of actual treatment will be calculated as (Last Dose Date of carfilzomib – First Dose Date of carfilzomib + i) / 7. When the last cycle is among cycles 1 to 12, i = 7 if the last infusion is given on day 1 or 8 within the last cycle, i = 14 if the last infusion is given on day 15. When the last cycle is among cycles 13+, i = 14 if the last infusion is given on day 1 or day 15 within the last cycle.

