Appendix A. Handling of Dates, Incomplete Dates and Missing Dates

A1. Imputation Rules for Adverse Events and Concomitant Medications (other than the new anti-myeloma therapy) dates

Imputation Rules for Partial or Missing Start Dates

The reference date for the following rules is the date of first dose.

Start Date		Stop Date						
		Complete: yyyymmdd		Partial: yyyymm		Partial: yyyy		Missing
		< 1st dose	≥ 1st dose	< 1st dose yyyym m	≥ 1st dose yyyy mm	< 1st dose yyyy	≥ 1st dose yyyy	
Partial: yyyym m	= 1st dose yyyymm	2	1	n/a	1	n/a	1	1
	≠ 1st dose yyyymm		2	2	2	2	2	2
Partial: yyyy	= 1st dose yyyy	3	1	3	1	n/a	1	1
	≠ 1st dose yyyy		3		3	3	3	3
Missing		4	1	4	1	4	1	1

1=Impute the date of first dose; 2=Impute the first of the month; 3=Impute January 1 of the year; 4=Impute January 1 of the stop year

Note: For subjects who were never treated (first dose date is missing), partial start dates will be set to the first day of the partial month or first day of year if month is also missing.

Imputation Rules for Partial or Missing Stop Dates

Initial imputation

- If the month and year are present, impute the last day of that month.
- If only the year is present, impute December 31 of that year.
- If the stop date is entirely missing, assume the event or medication is ongoing.
- If the imputed stop date is before the start date, set stop date to missing.

- If the imputed stop date is after the death date, impute as death date.

A2. Imputation Rules for New Antimyeloma Therapy Start Date

If the start day of new antimyeloma therapy is missing and month and year are not the same as last dosing date of study treatment, it will be assumed to be the first day of the month. If the start day of new antimyeloma therapy is missing and month and year are same as last dosing date of study treatment, the start date will be assumed as last dosing date of study treatment. In other situations, do not impute.

A3. Imputation Rules for Partial or Missing Death Dates

If death year and month are available but day is missing:

- If yyyyymm for the date last known to be alive equals yyyyymm for death date, set death date to the day after the date last known to be alive.
- If yyyyymm for the date last known to be alive is less than the yyyyymm for death date, set death date to the first day of the death month.
- If yyyyymm for the date last known to be alive is greater than yyyyymm for death date, assume death date is in error, do not impute and censor the subject survival time.

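### SAP Appendix A2 dates a new therapy with a missing day without regard to progression, so a same-month progression can be censored in PFS and DOR

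*SAP*

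**What the plan says.** SAP Appendix A2 covers a new-therapy start date that lacks only the day.

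- **Month differs from that of the last study dose:** "it will be assumed to be the first day of the month".
- **Month is the same as that of the last study dose:** "the start date will be assumed as last dosing date of study treatment. In other situations, do not impute".

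SAP Section 5 defines a PFS event as progression or death, "whichever occurs first in the absence of subsequent anticancer therapy". The event row of Table 5-1 reads "PD or death, no prior new anticancer therapy". If new therapy comes first, PFS is censored at the last evaluable assessment before it. The same section states that "DOR will be censored as per the PFS endpoint". Disease is assessed "every 28 ± 7 days from cycle 1 day 1" (SAP Section 3.1).

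SAP Table 9-2 lists PFS sensitivity analyses by assessor (investigator, ORCA) and by population (per protocol, modified safety). For DOR it varies the assessor only. SAP Section 8.3 leaves any other sensitivity analysis open.

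**The concern.** The planned order of events is progression first and new therapy second: subjects may be treated until progression, and other antimyeloma treatment is prohibited meanwhile (Protocol Sections 5.1 and 7.1.7.4). Both A2 branches pick an early date in the recorded month and never compare it with the progression date. A subject who progressed and switched later in that month can therefore be recorded as having switched first, and the progression drops out.

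Other parts of Appendix A do bound imputed dates by known ones. Imputed stop dates are capped at death (A1), and death dates are placed after the subject was last known alive (A3). A2 has no such check against progression. PFS also feeds the nine subgroup factors in SAP Section 4.2 and the MRD-by-PFS analysis in Section 9.5.3, so a lost event would carry into those as well.

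**Working it through.** The documents attach no figure to this rule, so there is none to reproduce. The check traces dates through the rules and then shows how the size depends on assumptions.

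**1. Worked dates (hypothetical).** Cycle 1 day 1 is 4 Jan 2021, with visits every 28 days. Progression is documented on 16 Aug (day 224). New therapy truly starts on 24 Aug, but the day is not recorded. SAP Section 5 gives months = (days + 1)/30.4.

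- True order: event at (224 + 1)/30.4 = 7.40 months.
- First branch, last dose 17 Jul: imputed start 1 Aug, before progression. Censored at the 19 Jul visit (day 196): (196 + 1)/30.4 = 6.48 months.
- Second branch, last dose 9 Aug: imputed start 9 Aug, before progression. Again censored at 6.48 months.

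**2. How often a day-missing record flips (first branch).** Assume a 30-day month, progression day d uniform on 1 to 30, and a switch g days later. A flip needs d + g ≤ 30 (same month) and d > 1, so its probability is max(0, 29 − g)/30.

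| g (days) | 3 | 7 | 14 | 21 | 28 |
|---|---|---|---|---|---|
| Flip | 87% | 73% | 50% | 27% | 3% |

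Averaged over a range of lags: 68% for 3–14 days, 50% for 7–21, 18% for 14–35 and 8% for 21–35.

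In the second branch, every progression after the last dose flips if dose, progression and switch share a month.

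**3. Illustrative size.** Simulation with n = 52 (SAP Section 3.2), exponential PFS, 28-day visits, follow-up uniform over 12–24 months, every event a progression followed by a switch, and the first-branch rule throughout. Only n and the visit interval come from the documents. With a true median of 10 months there are about 36 events. Each cell gives mean events lost and the rise in mean estimated median PFS in months.

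| Day missing | Lag 1–28 days | Lag 14–35 days | Lag 21–35 days |
|---|---|---|---|
| 5% | 0.9; 0.3 | 0.3; 0.1 | 0.2; under 0.1 |
| 10% | 1.8; 0.7 | 0.7; 0.3 | 0.3; 0.1 |
| 20% | 3.6; 1.3–1.4 | 1.4; 0.5–0.6 | 0.6; 0.2 |

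Hand check of one cell: 36 × 0.20 × 0.18 = 1.3 events.

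At a lag of 1–28 days with true medians of 7 or 17 months, losses run from about 0.6 to 4.2 events and the rise from about 0.3 to 1.0 months. With a true median of 10 months, 90% of simulated medians without any misdating fall between 7.4 and 13.8 months.

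**4. Direction.** A therapy that truly came before progression stays before it under either branch, provided it did not start before the last study dose. Day-missing imputation can therefore remove events but not create them.

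**The case against.** **Partial dates may be rare.** New therapy has its own CRF (listed in SAP Section 5), data are source-verified (Protocol Appendix 3), and subjects off drug report new treatment every 28 ± 7 days. This stands in part, since no document supports any particular rate. But the 28-day reporting stops at confirmed progression. After that, follow-up is every 12 weeks (Protocol Section 5.1), and these are largely the subjects at issue.

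**The switch lag may be long.** PFS runs to the first documentation of progression, and every effort should be made to obtain two consecutive assessments before new therapy (Protocol Section 9.2.2.6). If confirmation waits for the next scheduled visit, the lag is about 21–35 days and only 8% of day-missing records flip. This stands as a reason not to rely on short lags. However, no minimum interval between the two assessments is set, and the confirming sample may be taken after new therapy starts, so short lags are allowed.

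**Nothing tested depends on it.** The two hypotheses concern ORR and MRD[-]CR at 12 months. This stands. A reader might infer that ORR is affected too, because responses must be confirmed before new therapy. The documents do not support that: the IRC works from eCRF disease parameters (Protocol Section 9.2.2.1), and nothing says it uses dates imputed under the SAP.

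**Not every partial date loses events.** This also stands. A start date with the month missing is not imputed, and the SAP does not say how such a record enters the censoring. A progression after the switch might then count as an event, so a one-way bias cannot be claimed for all incomplete dates.

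**Conclusion.** The rule as written gives a wrong result in a definable case: day missing, progression and true switch in the same month, and progression after the imputed date but before the true switch. A true PFS or DOR event then becomes a censoring, about one visit interval earlier in the worked example. For day-missing dates the bias is upward, and no analysis in Table 9-2 offsets it.

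A reader might want to attach a fixed bias to the median. The documents do not allow it, because they give neither the number of partial dates nor the switch lag. The range of under 1 to about 4 lost events among 52 subjects rests on assumed rates of 5–20% and the lags shown, and does not model the second branch. In most of these scenarios the shift is small beside the sampling spread of the median. The point is worth correcting because the error is systematic and cheap to remove. It does not threaten the trial's tested conclusions.

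**What to change.** In Appendix A2, when only the day is missing, impute the latest of:

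- the first of the recorded month;
- the last study dose date;
- the day after progression, if progression by the assessor being analysed (IRC, investigator or ORCA) falls in that month.

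Cap the result at the last day of the recorded month. State that a progression on the same date as an imputed start counts as an event. The cap and the tie rule are needed together: a progression on 31 August with therapy recorded in August would otherwise be pushed into September. In both worked cases the imputed start becomes 17 Aug and the event returns to 7.40 months.

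Add a listing of subjects whose PFS or DOR status depends on an imputed start date.

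The cost is two or three sentences, a date derivation that may differ by assessor, and one listing. The downside is that a rare subject who truly switched shortly before a same-month progression is counted as an event. The listing makes such subjects visible.

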10.2.4 Handling of Missing and Incomplete Data

Subjects may have missing data points for various reasons and the impact on the analysis might differ from 1 endpoint to another. The general rules for accommodating the missing or incomplete data may be refined during the review of the data, and they will be described in detail in the statistical analysis plan (SAP). Sensitivity analyses might be needed to evaluate the robustness of the primary analysis results in case of significant missing data. Incomplete dates for the start of adverse event, concomitant medications, and death will be imputed and the detailed rules will be specified in the SAP.

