	
period of maintaining MRD[-]CR can have a window of ± 4 weeks, ie maintaining MRD[-]CR for at least 12 months (- 4 weeks) is considered as sustained.
 
Sustained MRD[-]CR at 24 months ± 4 weeks
 
Sustained MRD[-]CR rate at 24 months ± 4 weeks is defined as the proportion of subjects that maintain MRD[-]CR for 12 months or more after achieving MRD[-]CR status at their first MRD assessment at 12 months landmark.
 
It will be calculated along with the associated 90% and 95% exact binomial CIs that will be estimated using the Clopper-Pearson method. The 12 month period of maintaining MRD[-]CR can have a window of ± 4 weeks, ie, maintaining MRD[-]CR for at least 12 months (- 4 weeks) is considered as sustained.
 
Duration of Response (DOR)
 
Duration of response will be calculated for subjects who achieve sCR, CR, VGPR, or PR from the first date of PR or better to the date of disease progression or death due to any cause. If a subject is alive or lost to follow-up without experiencing documented disease progression by the data cutoff date, the DOR for the subject will be censored at the date of last valid disease and response assessment. The distribution of DOR including the median will be characterized using the Kaplan-Meier method based on the subjects who achieve best overall response of sCR, CR, VGPR or PR.
 
Time to Response
 
Time to response will be summarized with the non-missing sample size (n), mean, standard deviation, median, minimum, and maximum for responders, ie, subjects who achieve best overall response of sCR, CR, VGPR, or PR.
 
Progression Free Survival (PFS)
 
Progression Free Survival will be calculated from the time of start of treatment until disease progression or death due to any cause, whichever occurs first. If a subject is alive or lost to follow-up without experiencing documented disease progression by the data cutoff date, the PFS data for the subject will be censored at the date of last valid disease and response assessment. Detailed PFS data censoring rule will be described in the SAP. The distribution of PFS, including median, will be estimated using the Kaplan-Meier method. PFS rate at the selected time points (12 months and 24 months) will be reported. The 90% and 95% CIs for the median and other percentiles of PFS will be constructed using the method of Klein and Moeschberger (1997) with log-log transformation. The 90% and 95% CIs for PFS rates will be estimated using the methods by Kalbfleisch and Prentice (1980) with log-log transformation.
 
Overall Survival (OS)
 
Overall survival will be calculated from date of start of treatment until death due to any cause. Subjects still alive will be censored at the date last known to be alive.
 
OS will be analyzed using the same method as described for the PFS endpoints.
 
Complete Response or better rate (CR)
 
The CR will be analyzed using the same methods as described for ORR.

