International Staging System (ISS) Stage at Baseline

ISS stage at baseline will be calculated using serum beta-2 microglobulin and serum albumin values collected at baseline, based on the criteria published by the International Myeloma Working Group ([Greipp 2005](#)):

Stage I: Serum beta-2 microglobulin < 3.5 mg/L and serum albumin ≥ 3.5 g/dL

Stage II: Serum beta-2 microglobulin < 3.5 mg/L and serum albumin < 3.5 g/dL or Serum beta-2 microglobulin 3.5–<5.5 mg/L irrespective of the serum albumin

Stage III: Serum beta-2 microglobulin ≥ 5.5 mg/L

Last known to be alive date

Last known alive date is the latest date of the following dates before death date:

- Date First Taken, Date Last Taken on Concomitant Medications, **and Other Protocol Required Therapy** CRFs
- Date Performed on ECOG Performance Status, Vital Signs, Echocardiogram, Electrocardiogram, Transfusions, Surgery, Procedure, **Bone Marrow Biopsy - Multiple Myeloma, Bone Marrow Aspirate - Multiple Myeloma, MRI, PET-CT, CT and X-ray** CRFs
- Admission Date, Discharge Date on Hospitalizations, CRF Date of Examination on Physical Measurement CRF
- Date Collected on **Male Reproductive Status**, Reproductive Status and Pregnancy Test (Local Lab), Chemistry (Local Lab), Hematology (Local Lab), Coagulation (Local Lab), **Immunology (Local Lab)** CRFs
- Start Date, Stop Date on Investigational Product Administration (**Carfilzomib**), **Non-Investigational Product Administration (Dexamethasone)**, **Investigational Product Administration (Pomalidomide)**, and **Non-Investigational Product Administration (Pomalidomide)** CRFs
- Date Started and Date Ended or Resulted in Death on Events CRF
- Start date, Stop date on Anti-Myeloma / Anti-Cancer Therapies **CRF**
- Subject Status Date if status is Alive on Survival Status CRF
- Assessment Date on Skeletal Survey and Plasmacytoma Assessment CRF
- **Assessment Date for MRD sample**
- **Date Collected on Pathology FISH CRF**
- **Date of Assessment on Myeloma Response CRF**
- **Date of Last Menstrual Period and Breastfeeding Start in Reproductive Status and Pregnancy Test (Local Lab) CRF**
- **COVID-19 Start Date in Confirmed COVID-19 Status CRF**

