- **Date Decision Was Made to End Investigational Product on End of Investigational Product Administration (Carfilzomib), Date Decision Was Made to End Non-Investigational Product on End of Non-Investigational, Product Administration (Dexamethasone), End of Investigational Product Administration (Pomalidomide) and End of Non-Investigational Product Administration (Pomalidomide) CRFs, where the Primary Reason for ending treatment is not Death or Lost to follow-up**

MRD[-]ICR

MRD[-]ICR is defined as achievement of CR (including sCR) per IMWG-URC and MRD[-] status at a sensitivity of 10^{-5} using next generation sequencing (NGS) based method in the bone marrow at any time.

MRD[-]ICR Rate at 12 Months Landmark

MRD[-]CR rate at 12 months landmark is defined as proportion of subjects who reach MRD[-]CR at 12 months landmark assessment among all subjects who received at least 1 dose of carfilzomib. **The sensitivity analysis of MRD[-]CR Rate at 12 months landmark will be based on MRD Evaluable Analysis Set.** The data will include the MRD results from bone marrow samples obtained from subjects with Suspected CR or better obtained no earlier than 8 months and no later than 12 months plus 4 weeks after the start of any study treatment.

MRD[-] Rate at Any Time During Therapy

MRD[-] rate at any time during therapy is defined as proportion of subjects who reach MRD[-] at any time during therapy among all subjects who received at least 1 dose of carfilzomib. **The sensitivity analysis of MRD[-]CR Rate at any time during therapy will be based on MRD Evaluable Analysis Set.** The data will include the MRD results from bone marrow samples obtained from the subjects with a response of VGPR or better at any time during therapy.

Number of cycles started for any study drug

It is defined as the total number of treatment cycles in which at least one dose of any study drug is administered.

Number of cycles started for each study drug

It is defined as the total number of treatment cycles in which at least one dose of carfilzomib/pomalidomide/dexamethasone, respectively, is administered.

Number of cycles started for all study drugs

It is defined as the total number of treatment cycles in which at least one dose of carfilzomib, one dose of pomalidomide and one dose of dexamethasone is administered.

Number of doses of carfilzomib administered

It is defined as the total number of non-zero doses of carfilzomib a subject received during the treatment period of the study

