If month and day are missing and year of death is known:

- If yyyy for the date last known to be alive equals yyyy for death date, set death date to the day after last known to be alive date.
- If yyyy for the date last known to be alive is less than yyyy for death date, set death date to the first day of the death year.
- If yyyy for the date last known to be alive is greater than yyyy for death date, assume death date is in error, do not impute and censor the subject survival time.

If a death date is totally missing:

Do not impute and censor the subject survival time.

A4. Imputation Rules for Dates of Prior Multiple Myeloma Therapy and Relapse/progression to Prior Multiple Myeloma Therapy:

If the day of prior multiple myeloma therapy or relapse/progression to prior multiple myeloma therapy is missing but month and year are available, then impute the date to 15th of the month. If month or year is missing or the date is completely missing, do not impute.

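### SAP Appendix A3 censors overall survival for a subject known to have died when the death date is totally missing, contrary to the plan's own OS definition and biasing OS upward

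*SAP*

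**What the plan says.** SAP Section 5 gives the endpoint: "OS is defined as time from start of treatment until death from any cause". Protocol Section 10.4.2.2 and SAP Section 5 give the same censoring rule: "Subjects still alive will be censored at the date last known to be alive". Protocol Section 10.2.4 adds: "Incomplete dates for the start of adverse event, concomitant medications, and death will be imputed", and leaves the detailed rules to the SAP.

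SAP Appendix A3 supplies those rules, in three branches:

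- **Partial date compatible with the last-alive date.** The death stays an event. If the known month or year is the same as that of the last-alive date, the rule is to "set death date to the day after the date last known to be alive". If it is later, the first day of the death month or year is used.
- **Partial date in an earlier month or year than the last-alive date.** The rule is to "assume death date is in error, do not impute and censor the subject survival time".
- **Date totally missing.** The rule is "do not impute and censor the subject survival time". No censoring date is named.

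The last-known-alive date is defined in SAP Section 5 as the latest of a list of CRF dates that precede death. One item on the list is "Date Started and Date Ended or Resulted in Death on Events CRF". The end-of-treatment item, by contrast, carries the restriction "where the Primary Reason for ending treatment is not Death or Lost to follow-up".

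**The concern.** A subject with a recorded but undated death is not still alive, so the OS censoring rule does not cover that subject. A3 censors the subject anyway, and the reason for censoring is the event that OS is meant to measure. Such censoring is informative. It removes an event, so it pushes the Kaplan-Meier curve up.

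A3 is also uneven. With only a year of death known, the true date may be uncertain by up to about a year, yet the death is kept as an event. With no date, the death is dropped, although the day-after-last-alive rule could be applied just as easily.

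At stake are the OS landmark estimates and the median, which readers may set beside the results of earlier KPd trials.

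**Working it through.** **1. Does another part of the plan correct this?** SAP Table 9-2 lists two OS sensitivity analyses, per-protocol and modified safety population. Both change who is analysed and neither changes how an undated death is scored. SAP Section 10 lists death among the dates to be imputed and does not mention that some recorded deaths are censored.

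**2. Does any stated figure depend on A3?** No. The plan gives no OS event count or power. The eight power figures in SAP Table 3-1 reproduce by exact binomial calculation. With n = 52 and an ORR reference of 60%, the smallest count whose Clopper-Pearson 90% lower bound exceeds the reference is 38, and power at 80% is 91.8%. For MRD[-]CR against 3% the count is 5, and power at 12% is 76.3%. No death date enters these.

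**3. Size by hand.** Suppose no one else is censored before month 24 and the affected subject died before then, with n at risk. Censoring just before death removes the factor (1 − 1/n), so S(24) is multiplied by n/(n − 1) and rises by S(24)/(n − 1).

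- S(24) = 0.445, first death of 52: 0.445/51 = 0.9 points. With 26 at risk: 0.445/25 = 1.8 points.
- S(24) = 0.767, first death of 52: 0.767/51 = 1.5 points. With 42 at risk: 0.767/41 = 1.9 points.
- A death after month 24 leaves S(24) unchanged if last contact was also after month 24.

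Averaging over early and late deaths gives roughly 1 point.

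**4. Size by simulation.** Inputs from the documents: 52 treated subjects, 12-weekly survival contact, and earlier KPd results in Protocol Table 5-1 (median OS 20.6 months; 67% alive at 12 months; 77% alive at 24 months). Assumptions: exponential OS, minimum follow-up of 12 or 48 months plus a 0 to 20 month accrual spread, last contact 0 to 12 weeks before death, and 1 or 3 affected deaths. There were 3000 runs per row.

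| Assumed OS | Min. follow-up (months) | Mean deaths | S(24), all counted | 1 censored | 3 censored | Rise in points (1; 3) |
|---|---|---|---|---|---|---|
| median 20.6 months | 12 | 26.8 | 0.446 | 0.459 | 0.486 | 1.3; 4.0 |
| median 20.6 months | 48 | 44.5 | 0.445 | 0.454 | 0.469 | 0.9; 2.4 |
| 67% at 12 months | 12 | 26.6 | 0.449 | 0.461 | 0.490 | 1.2; 4.1 |
| 67% at 12 months | 48 | 44.3 | 0.449 | 0.457 | 0.471 | 0.8; 2.2 |
| 77% at 24 months | 12 | 11.0 | 0.769 | 0.787 | 0.827 | 1.8; 5.8 |
| 77% at 24 months | 48 | 24.5 | 0.767 | 0.778 | 0.794 | 1.1; 2.7 |

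The columns come from separate draws, so single differences carry some simulation noise. In the four rows with a median near 20 months, one censored death adds 0.6 to 0.8 months to the median and three add 1.9 to 2.6 months.

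**5. Does the day-after rule do better?** A second design used medians of 20.6, 30 and 40 months with follow-up of 24 to 48 months. The error in 24-month OS per affected death depends on the gap between last contact and death:

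| Gap | A3 (censor) | Event on day after last alive |
|---|---|---|
| 0 to 12 weeks | +0.9 to +1.1 points | less than 0.2 points, downward |
| 6 to 24 months | +0.6 to +1.0 points | −0.3 to −0.5 points |

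The day-after rule is less biased in both cases. It errs downward because it uses the earliest possible date.

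**The case against.** **The censoring rule does not say that only living subjects are censored, and the protocol promises imputation of incomplete dates, which need not mean absent ones.** Both readings are fair. They leave the OS definition untouched, and a subject with a recorded death still does not fit a rule written for subjects still alive.

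**A wholly missing date offers nothing to anchor an imputation.** The last-alive date is an anchor, and A3 already uses it for some partial dates.

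**Undated deaths should be rare.** Protocol Section 9.2.4.9 requires the date of death. Serious events are collected through long-term follow-up (Section 9.2.4.1.2), and grade 5 events are separate one-day records (Appendix 4). This stands and limits the likely count.

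**The effect is small.** The sampling SD of 24-month OS in the second design is about 6.5 to 7 points, against about 1 point per affected death, and OS is untested. This also stands.

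Four stronger readings are tempting but not supported:

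- *PFS is biased too.* A3 speaks only of survival time. PFS has its own rules in SAP Table 5-1, which already censor deaths after new anticancer therapy or more than 70 days after the last evaluable assessment. No PFS effect has been shown.
- *Conflicting partial dates are an equal problem.* Since the last-alive date is limited to dates preceding death, that branch is almost unreachable. If it were reached, the file might hold evidence of life after the recorded death, so the death itself could be in question.
- *A dated fatal event would be censored on the day of death.* This assumes that a complete fatal-event date on the Events CRF does not count as a death date. The documents do not say so; the wording is merely unclear.
- *The deaths are counted as survivors.* They are censored and leave the risk set.

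**Conclusion.** The point holds for OS and for the totally missing date. Following A3 as written turns a known death into an informatively censored time, contrary to the SAP's own definition, with nothing planned to correct it. The bias is upward, at roughly 1 percentage point in 24-month OS per affected death (0.8 to 1.8 in the first set of scenarios) and 2.2 to 5.8 points for three. These figures rest on exponential survival, the assumed follow-up and a short gap between last contact and death; with a gap of 6 to 24 months the rise is 0.6 to 1.0 points per death. The number of such deaths is not in the documents; 1 to 3 is an assumption, and if there are none the effect is nil. Importance is limited, because OS is a descriptive secondary endpoint in a single arm of 52 and neither tested endpoint is touched. The correction is still worth making, since the rule is plainly at odds with the estimand and cheap to change.

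**What to change.** Amend SAP Appendix A3 and the related definitions:

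1. Count a known death with a totally missing date as an OS event. Date it from a complete fatal-event date on the Events CRF if one exists, otherwise on the day after the date last known to be alive.
2. Report how many deaths are dated this way. Add an OS sensitivity analysis using a later plausible date, for example the date on which the death was first reported to the study.
3. In the SAP Section 5 list, state that the date on which an event resulted in death is a death date and cannot serve as a last-known-alive date.
4. Reconcile the conflicting-partial-date branch with the restriction of the last-alive date to dates preceding death. Require a data query before any such subject is censored, and name the censoring date if censoring is kept.
5. State whether A3 applies to PFS and DOR.

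The cost is a few lines of SAP text, one programming rule and one extra output. No sample size, test or decision rule changes. Reported OS becomes slightly less favourable if such a death exists.
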